### **6.2.3 Baseline**

Baseline is defined as the last non-missing value (either scheduled, unscheduled or repeat) before the subject receives the first dose of study drug. The same baseline will be used for all SAD, MAD and MAD extension parts using the last available records before first dose of study drug in SAD part.

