### **6.2.6 Conventions for Missing and Partial Dates**

It is not expected that there will be any missing dates, however in the rare case that an AE start date or time is missing and it is unclear whether the AE is treatment emergent or not then a conservative approach will be taken and it will be assumed that the AE occurred after first dosing (earliest date of all doses during the whole study).

Partial or missing stop date will be imputed as follows:

If the stop date is completely missing and the event has resolved, or the subject has stopped taking the concomitant medication, the stop date will be imputed as the date of the subject's end of study visit

- If only the year is known, the stop date will be imputed as "31-Dec" of that year or as the date of the subject's last clinic visit in the study if in the same year.
- If the month and year are known, the stop date will be imputed as the last day of that month unless the stop date corresponds to the same month as the subject's last clinic visit in which case the date of subject's last clinic visit in the study will be used instead.

Missing start date will be imputed as follows:

- If the stop date occurs on or after the start of study drug or the event / concomitant medication is ongoing, the start date will be imputed as the date of the first dose of study drug.
- If the stop date occurs before the start of study drug, the start date of the event / concomitant medication will be imputed as the subject's screening date or the stop date of the event / concomitant medication whichever the earlier.

Partial start date (year present, but month and day missing) will be imputed as follows:

- If the stop date occurs on or after the start of study drug or the event / concomitant medication is ongoing, and the year is the same as the year of first dosing the start date will be imputed as "01-Jan" of the same year or the date of the first dose of study drug whichever is latest. If the year is different from the year of first dosing "01-Jan" will be used.
- If the stop date occurs before the start of study drug, the start date of the event / concomitant medication will be imputed as the "01-Jan" of the same year.

Partial start date (month and year present, but day missing) will be imputed as follows:

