### 6.2.7 Exposure to Study Drug

Exposure to study drug will be calculated separately for SAD and MAD + MAD Extension parts.

**SAD part:** exposure will be set to 1 if subject was dosed.

**MAD + MAD Extension part:** date of last MAD dosing - date of first MAD dosing + 1.

The exposure calculation will not take into account breaks in therapy.

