### **6.14.1 Adverse Events**

Adverse events will be reported separately for SAD and MAD + MAD Extension parts.

A pre-therapy AE is defined as any AE that starts before the first dose of study drug.

A treatment emergent adverse event (TEAE) is defined as:

- Any AE that has an onset on or after the first dose of study drug and before last dose of study drug + 28 days.
- Any pre-existing AE that has worsened in severity on or after the first dose of study drug and before the last dose of study drug + 28 days.

A treatment-related AE is defined as an AE as being related to the study drug. If an AE has missing relationship it is assumed to be related to the study drug for analysis purposes.

Maximum severity will be assumed for an AE with missing severity.

The following tables will be presented for AEs:

- Summary of All Adverse Events, incidence and the number of events.
- Pre-therapy AEs by system organ class and preferred term, incidence and number of events
- TEAEs by system organ class and preferred term, incidence and number of events
- Treatment-related TEAEs by system organ class and preferred term, incidence and number of events

- Serious TEAEs by system organ class and preferred term, incidence and number of events
- TEAEs leading to treatment withdrawal by system organ class and preferred term, incidence and number of events
- All AEs of special interest by system organ class and preferred term, incidence and number of events
- TEAEs by system organ class, preferred term and maximum severity, incidence
- Treatment related TEAEs by system organ class, preferred term and maximum severity, incidence
- TEAEs by system organ class, preferred term and study drug relationship, incidence
- Listing of Deaths (presented in the Table section of the appendices)
- Listing of Serious TEAEs (presented in the Table section of the appendices)

All AEs will be listed.

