14.2.4.1	GAS Questionnaire, Frequency Table – Pharmacokinetic Set		IP	14.2.2.1
14.2.4.1	GAS Questionnaire, Responders – Pharmacokinetic Set		IP	14.2.2.1
14.2.5.1	Respiratory Function Tests, Descriptive Statistics – Pharmacokinetic Set	4	IP	14.2.1.1
14.2.5.2	Respiratory Function Tests, Shift Table – Pharmacokinetic Set	4	IP	
14.2.5.3	Explorative Bayesian Analysis for Respiratory Function Tests – Pharmacokinetic Set		Stat IP	
14.2.6.1	MyoGrip, Descriptive Statistics – Pharmacokinetic Set	4	IP	14.2.1.1
14.2.6.2	Explorative Bayesian Analysis for MyoGrip – Pharmacokinetic Set		Stat IP	14.2.5.3
14.2.7.1	MFM32, Descriptive Statistics – Pharmacokinetic Set	4	IP	14.2.1.1
14.2.7.2	Explorative Bayesian Analysis for MFM32 – Pharmacokinetic Set		Stat IP	14.2.5.3
14.2.8.1	Dysphagia Questionnaire, Descriptive Statistics – Pharmacokinetic Set	4	IP	14.2.1.1
14.2.9.1	Muscle Biopsy, Descriptive Statistics – Pharmacokinetic Set	4	IP	14.2.1.1
14.3	Safety Data			
14.3.1	Displays of Adverse Events			
14.3.1.1.1	Overall Summary of Adverse Events – Safety Analysis Set	1-4	IP	
14.3.1.2.1	Pre-Therapy AEs by System Organ Class and Preferred Term – Safety Analysis Set	1-4	IP	
14.3.1.2.2	TEAEs by System Organ Class and Preferred Term – Safety Analysis Set	1-4	IP	14.3.1.2.1
14.3.1.2.3	Treatment Related TEAEs by System Organ Class and Preferred Term – Safety Analysis Set	1-4	IP	14.3.1.2.1
14.3.1.2.4	Serious TEAEs by System Organ Class and Preferred Term – Safety Analysis Set	1-4	IP	14.3.1.2.1
14.3.1.2.5	TEAEs Leading to Treatment Withdrawal by System Organ Class and Preferred Term – Safety Analysis Set	1-4	IP	14.3.1.2.1
14.3.1.2.6	All AEs of Special Interest by System Organ Class and Preferred Term – Safety Analysis Set	1-4	IP	14.3.1.2.1

Table Number	Table Title	Included in IDMC meetings	Validation Method	Shell Number (if repeat)
14.3.1.3.1	TEAEs by System Organ Class, Preferred Term and Maximum Severity – Safety Analysis Set	1-4	IP	
14.3.1.3.2	Treatment Related TEAEs System Organ Class, Preferred Term and Maximum Severity – Safety Analysis Set	1-4	IP	14.3.1.3.1
14.3.1.4.1	TEAEs by System Organ Class, Preferred Term and Strongest Study Drug Relationship – Safety Analysis Set	1-4	IP	
14.3.2	Listings of Deaths, Other Serious and Significant Adverse Events			
14.3.2.1	Listing of Deaths – Safety Analysis Set	1-4	IP	
14.3.2.2	Listing of Serious TEAEs – Safety Analysis Set	1-4	IP	14.3.2.1

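### The TEAE cut-off before last dose + 28 days keeps late serious or related events out of the serious-event and treatment-related outputs, although AEs are collected for 3 months after the last dose

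*SAP*

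**What the plan says.** SAP 6.14.1 defines a TEAE as an AE with onset "on or after the first dose of study drug and before last dose of study drug + 28 days". The same limit applies to worsening of a pre-existing AE. The section then names 12 AE outputs and adds that every AE goes into a listing (Listing 16.2.7.1 in SAP 12). The serious-event table, the serious-event listing and both treatment-related tables (by SOC/PT, and by maximum severity) are restricted to TEAEs. The AESI table and the deaths listing are not. The first output is a "Summary of All Adverse Events, incidence and the number of events", which SAP 12 titles "Overall Summary of Adverse Events" (Table 14.3.1.1.1). Its shell is not shown.

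On reporting by part, 6.14.1 says "Adverse events will be reported separately for SAD and MAD + MAD Extension parts". It does not say whether last dose means the last dose of a part or of the study.

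The protocol collects AEs and SAEs from main consent to the last trial visit (6.2.2.1, 7.6, 7.7). The Synopsis places that visit 3 months after the last IMP administration. Protocol 9.8 uses the term TEAE without a window and allows related AEs and SAEs to be either summarised or listed.

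**The concern.** The primary endpoint (SAP 3.1) is the frequency and severity of AEs, SAEs and AESIs by cohort, and it includes subjects who stopped early. For those subjects, the protocol goes on collecting events well after the point at which the SAP stops counting them. Protocol 7.5.2 treats responses as related unless another cause is reasonable, so investigators may well mark a late event as related. That event would then be missing from the table of related events.

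The SAP gives pre-therapy AEs their own SOC/PT table, whereas events after the window get none unless they are AESIs.

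The trial was terminated early, and under SAP 8 the report reuses the IDMC safety outputs, so these tables carry much of the by-cohort AE evidence.

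The cut-off also makes an event's status depend on whether the subject is dosed again later, which can distort counts between groups with different continuation.

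**Working it through.** **1. Which outputs carry the limit (SAP 6.14.1, checked against SAP 12).**
- Not limited to TEAEs: overall summary, pre-therapy AEs, AESIs, deaths = 4.
- Limited: TEAEs by SOC/PT; related; serious; leading to withdrawal; by maximum severity; related by maximum severity; by relationship; serious listing = 8. Total 4 + 8 = 12.
- An event that starts after treatment has ended cannot cause withdrawal from treatment. In post-treatment follow-up, therefore, 8 − 1 = 7 outputs can lose events.

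**2. Trace one event.** Take a related, serious, non-fatal event that is not an AESI, 40 days after a subject's final dose. Since 40 > 28 it is not a TEAE. It is absent from the serious table, the serious listing, both related tables, and the SOC/PT, severity and relationship tables. It appears in Listing 16.2.7.1 and possibly in Table 14.3.1.1.1. If it were an AESI it would also be in the AESI table, which shows incidence and number of events but not severity. If fatal, it would be in the deaths listing.

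**3. Length of the gap.** Assume 3 months = 91 days: 91 − 28 = 63 days outside the window, and 63/91 = 69%. With 84 days it is 56/84 = 67%; with 92 days, 64/92 = 70%. These are shares of calendar time, not of events.

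**4. What last dose means.** The SAP's other anchors are study-wide:
- SAP 6.2.6 uses the "earliest date of all doses during the whole study".
- SAP 6.2.3 states "The same baseline will be used for all SAD, MAD and MAD extension parts".
- SAP 6.2.5 counts study days from the first SAD dose.
- When the SAP means one part it says so. MAD exposure in 6.2.7 is "date of last MAD dosing - date of first MAD dosing + 1".

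The study-wide reading is therefore the natural one.

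**5. Consequence for SAD washout on that reading.** A Day 60 event lies 60 − 1 = 59 days after the single dose.
- Subject who later starts MAD: the last dose comes later still, so the event is a TEAE.
- SAD-only subject: the window closes before Day 1 + 28 = Day 29, so the identical event is not a TEAE.

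For a SAD-only subject followed to Day 113 (112 days after dosing), 112 − 28 = 84 days are outside the window, and 84/112 = 75%. AEs are collected at 11 scheduled visits after Day 1 (Days 2, 3, 8, 15, 29, 43, 57, 71, 85, 99, 113). Six of them, Days 43 to 113, nominally cover only time after the cut. Protocol 6.1.3.2 asks for the washout visits even from subjects who do not go on to MAD.

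**6. Interruptions.** Protocol 7.11.2 foresees interruptions of more than 4 consecutive weeks. An event 35 days after the most recent dose is a TEAE if dosing resumes, and is not one if the interruption becomes permanent.

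**The case against.** **Late events are not lost.** This stands. All AEs are listed, AESIs (thrombocytopenia, hepatic and kidney impairment, vasculitis) have an unrestricted table, and deaths have an unrestricted listing. With about 18 subjects, a late SAE can be found by reading the listing. A listing still does not give the by-cohort comparison that the endpoint names, and a serious-event listing that omits a serious event invites misreading.

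**No rule is broken.** A reader might infer a breach of the protocol. The documents do not support that: the protocol sets no TEAE window and permits listing instead of summarising.

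**The window length is a convention.** A reader might infer from the pharmacokinetics that 28 days is too short. Protocol 1.3.1 gives a 21-day terminal half-life in monkeys, so 0.5^(28/21) = 40% of terminal-phase drug would remain at day 28 if that held in humans. The 2 to 4 weeks quoted for the class gives 25% to 50%. The same section reports 90% of steady state after 6 weeks, which under a single-exponential assumption gives 0.1^(28/42) = 22%. The figures are mixed, and residual drug does not by itself make a 28-day window wrong. A general change of window would be a preference.

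**Washout already belongs to SAD.** A reader might infer that washout events have no assigned part. SAP 1, Protocol 6.1.3.2 and the schedule's SAD week labels all place washout in the SAD part; only an explicit line in 6.14.1 is missing. A reader might also infer that every subject loses SAD events from Day 29. That follows only if last dose is read per part, which the SAP's other anchors do not favour.

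**Reach is limited.** Subjects on weekly dosing up to Week 25 are unaffected. This stands.

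**Conclusion.** The point holds in a narrow form. As written, a late serious or related event that is neither fatal nor an AESI misses every SOC/PT, severity and relationship table and the serious listing. On the study-wide reading, by-cohort counts also depend on later dosing.

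Those affected are early discontinuers, SAD-only subjects, subjects whose interruption becomes permanent, and post-treatment follow-up generally. The documents give neither the number of such subjects nor the number of events, so the effect on the results cannot be sized. The 69% and 75% describe follow-up time only, and the 69% assumes a 91-day follow-up that not every subject will complete.

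I rate it between minor and should-fix. The default is avoidable and the data are already collected, but nothing is hidden from someone who reads the full listing.

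**What to change.** In SAP 6.14.1:

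1. Extend the serious-event table, the listing of serious TEAEs and the treatment-related tables (including the one by maximum severity) to all such events from first dose to the last trial visit. Show the extended counts in a supplementary column beside the retained 28-day column; in the listing, flag events outside the 28-day window. Keeping the 28-day column preserves comparability with the IDMC outputs.
2. Report observed follow-up time per treatment group.
3. Add one line saying that last dose is the last dose of the whole study and that washout events are reported under SAD.

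The cost is a short SAP addition and a rerun of a few AE outputs. Counts will rise slightly, with more background events. Late ascertainment will be uneven, because the 3-month visit is by agreement for early discontinuers (Protocol 6.1.5) and applies otherwise only to subjects not continuing on IMP (Protocol 6.1.4); item 2 lets the reader judge this. The change comes late in an open-label, terminated trial, so the added column should be labelled supplementary. The general TEAE tables keep the 28-day window and therefore still depend on later dosing.

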9.8 Safety Analyses

Safety analyses will be presented for the Safety Analysis Set.

Baseline for all clinical laboratory tests, physical examination results, vital signs, liver ultrasound and hepatic elastography, and ECG will be defined as the last assessment prior to IMP administration.

Safety data will be analyzed using descriptive statistics (arithmetic mean, geometric mean, SD, %CV, median, minimum and maximum values, including 95% confidence intervals (CIs), if applicable).

Adverse Events

AEs will be coded using the MedDRA version available at the start of the trial. The number of events as well as the incidence and percentage of subjects with treatment-emergent adverse events (TEAEs) will be calculated overall, by system organ class, and by preferred term. TEAEs will be further summarized by severity and relationship to IMP. AEs related to IMP, AEs of special interest, AEs leading to withdrawal, SAEs and deaths will be summarized or listed.

Clinical Laboratory Tests

Descriptive statistics of observed values and changes from baseline will be calculated for each laboratory analyte at each scheduled time point. The frequency counts and percentage of subjects with laboratory abnormalities will be tabulated at each scheduled time point. The laboratory abnormalities will be determined according to the CTCAE criteria (version 5, November 2017) and in accordance with the normal ranges of the clinical laboratory if no gradings are available. Potentially clinically important findings will also be summarized or listed.

Physical Examination

Physical examination abnormalities will be listed at each scheduled time point.

Vital Signs and ECG

Descriptive statistics of observed values and changes from baseline will be calculated for each vital signs and ECG parameter at each scheduled time point. The frequency counts and percentage of subjects with abnormalities for each parameter will be tabulated at each scheduled time point.

Liver Ultrasound and Hepatic Elastography

The observed data for liver ultrasound and hepatic elastography assessments will be listed.

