### 3 ENDPOINTS

#### 3.1 Primary Endpoint

- Comparison of adverse event (AE, SAE, AESI) frequency and severity by dose (cohort), for single and multiple administration, and by mutated gene (subcohort) and overall using the Safety Analysis Set following 12 weeks of MAD treatment and after 24 weeks of MAD treatment (12 weeks in the MAD part + 12 weeks in the MAD extension part; Week 25 visit) or discontinued earlier.

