## **6.14 Safety Analyses**

The safety analyses (AE, clinical laboratory tests, physical examination, vital signs and ECG) will be presented by the treatment received for the Safety Analysis Set.

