## **8 PRIMARY AND FINAL ANALYSIS**

The study was terminated early and therefore planned primary and final analyses will not be performed. Reporting will include only same set of outputs as was delivered for the IDMC meetings (full safety analyses) and selected key efficacy endpoints. Section 12 of this SAP is updated to highlight which outputs are excluded from the planned.

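### The only AESI table pools events regardless of timing and shows no severity, although AESI frequency and severity by dose are part of the primary endpoint

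*SAP*

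**What the plan says.** The primary endpoint, in substance the same in Protocol 3.3.1 and SAP 3.1, is a "Comparison of adverse event (AE, SAE, AESI) frequency and severity by dose (cohort"), also split by single and multiple administration and by mutated gene, in the Safety Analysis Set.

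SAP 6.14.1 plans one table specific to AESIs: "All AEs of special interest by system organ class and preferred term, incidence and number of events". SAP 12 lists it as Table 14.3.1.2.6, "All AEs of Special Interest by System Organ Class and Preferred Term", for IDMC meetings 1 to 4. Severity is tabulated twice: "TEAEs by system organ class, preferred term and maximum severity, incidence" (Table 14.3.1.3.1), and the same layout for treatment-related TEAEs (Table 14.3.1.3.2).

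Two rules govern the display. Under SAP 6.14, safety results "will be presented by the treatment received for the Safety Analysis Set". Under SAP 6.14.1, "Adverse events will be reported separately for SAD and MAD + MAD Extension parts". A TEAE starts or worsens on or after the first dose and before last dose + 28 days.

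After early termination, SAP 8 states: "Reporting will include only same set of outputs as was delivered for the IDMC meetings (full safety analyses"). The AESI table therefore remains in the abbreviated report. Protocol 9.8 says that "TEAEs will be further summarized by severity and relationship to IMP", and lets AESIs be either summarized or listed.

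**The concern.** The endpoint asks for two things about AESIs by dose: how often and how severe. The AESI table answers the first with events of any timing and does not address the second.

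On timing, AEs are collected from main consent to the last trial visit (Protocol 6.2.2.1), which is wider than the TEAE window at both ends. The group labels in SAP 6.3 are dose-by-gene columns with none for the time before dosing. The split into SAD and MAD + extension does not say where a pre-dose or late AESI belongs. As worded, such an event is counted under a dose together with on-treatment events.

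On severity, an AESI is identified by a mark in the eCRF (Protocol 7.2), not by a preferred term. The two severity tables run by preferred term on TEAEs and are not described as carrying that mark.

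At stake is whether a reader of the report can see AESI frequency and severity by dose directly. The protocol's AESIs are thrombocytopenia, impaired hepatic function, impaired kidney function and vasculitis. Laboratory shift tables inform the first three, but there is no validated marker for vasculitis (Protocol 7.2).

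**Working it through.** **Count of planned AE tables (SAP 6.14.1).** 1 overall summary + 1 pre-therapy + 7 limited to TEAEs + 1 AESI = 10. AESI-specific tables: 1. Of these, limited to TEAEs: 0; showing severity: 0. Tables by maximum severity: 2. Of these, AESI-specific: 0. Deaths and serious TEAEs each also have their own listing in the table section; AESIs do not.

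**AE collection after the TEAE window.**
- Subject who attends the 3-month follow-up (Protocol 6.1.4), with 3 months taken as 91 days: 91 − 28 = 63 days. This visit does not apply to a subject who continues IMP after the trial.
- Subject who stops after the single dose: dosing is on Day 1, so last dose + 28 days is Day 29. Site visits continue to Day 113 even without progression to MAD (Protocol 6.1.3.2 and the SAD follow-up schedule): 113 − 29 = 84 days.

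**AE collection before first dose (Protocol 6.1.2).**
- Natural history study subject without run-in, screened within 6 weeks of baseline: 0 to 6 × 7 = 42 days.
- Subject with one run-in visit: at least 28 + 28 = 56 days.

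**Weight of one event.** Full cells hold up to 6 DNM2 or 3 MTM1 subjects per cohort. One subject with an AESI is 1/6 = 17% or 1/3 = 33%.

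**Whether late events could be drug effects.** Protocol 1.3.1 gives a terminal half-life of 21 days in monkeys. If it applied in humans, the fraction of the terminal-phase level left would be
- at 28 days: 2^(−28/21) = 0.40
- at 91 days: 2^(−91/21) = 0.05

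About 40% would remain when the TEAE window closes. Late AESIs are therefore informative and should be kept, but shown apart from on-treatment events.

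The documents give no AESI rate, so the expected number of off-window events cannot be calculated.

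**The case against.** The strongest reply is that this is a matter of layout in a descriptive trial, and much of it stands.

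- **The protocol is met.** Section 9.8 asks for TEAE severity and for AESIs to be summarized or listed. The SAP does both, lists all AEs, and allows further tables (SAP 6). A reader might infer a breach of the protocol; there is none.
- **Severity is recoverable.** A treatment-emergent AESI appears in Table 14.3.1.3.1 under its preferred term. With about 18 planned subjects, matching it to the AE listing is easy. A reader might infer that no output delivers AESI severity. The documents do not support that, and because the table shells are not available, an AESI line in the overall summary cannot be excluded.
- **Pre-dose AESIs are unlikely.** Entry requires platelets above 150,000/µL and no clinically significant liver or renal disease. Conditions found at screening go to medical history. Run-in laboratory tests are repeated only if screening results are more than 12 weeks old at baseline, so none is due in the 56-day (8-week) case. A subject with a confirmed low platelet count is not dosed, and a subject never dosed is outside the Safety Analysis Set. Any pre-dose AESI also appears in the pre-therapy table, which has the same column labels.
- **Counting all AESIs may be deliberate.** It captures late vasculitis, and Protocol 7.10 follows AESIs after the trial whatever their causality. A reader might infer that the table should simply be cut to TEAEs. That would lose the late events, which the half-life figure argues against.
- **AESIs are not alone.** The serious TEAE table also gives only incidence and number of events.

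What does not fall away is that a named component of the primary endpoint has to be assembled from several outputs, and that the one table bearing its name does not separate on-treatment from off-treatment events.

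**Conclusion.** The point holds as a minor one. Table 14.3.1.2.6 pools AESIs regardless of timing and gives no severity, while the primary endpoint names AESI frequency and severity by dose.

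The exposure to off-window events is mainly at the late end: about 63 days up to the 3-month visit, or 84 days of scheduled visits after a SAD-only course. A single such event would shift a full cell by 17 or 33 percentage points, but few are expected. The day counts measure opportunity, not harm.

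The conclusion rests on the table titles and text in SAP 6.14.1 and 12, on 3 months taken as 91 days, and on full planned cells. The 40% figure assumes that the monkey half-life carries over to humans; it supports only keeping the late events.

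**What to change.** Revise Table 14.3.1.2.6 so that its main body shows treatment-emergent AESIs by dose and sub-cohort, with number of subjects, number of events and maximum severity, separately for SAD and MAD + extension. Add two labelled rows, one for AESIs before first dose and one for AESIs from last dose + 28 days onward, so that nothing is dropped. The same maximum-severity column can be added to the serious TEAE table.

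The cost is reprogramming one retained table, plus one column in a second. The AESI mark, onset date and severity are already collected in the eCRF, so no new data are needed.
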